9. DESIGN AND RATIONALE

In both groups, and to enable both groups of subjects to access treatment for PE, the control will be intra-subject. The main variables and data to establish the baseline of each group will be collected during a period of a similar length to the treatment period.

-This research project will use two experimental groups. One will be given the "sct" therapy (experimental group 1) and the other will be given the "start-stop" therapy combined with the external device (experimental group 2). The two groups will receive parallel therapy with the same exercise protocol (with the only difference being that, in experimental group 2, the sct exercises will be carried out with the device in question). The participants who meet the selection criteria will be randomly assigned to an experimental group, along with its corresponding conditions.

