14. STATISTICAL ANALYSIS

As the main evaluation parameter, the "fold change" of the IELT will be used, which will be calculated using the geometric averages of the post-treatment IELT (period B) divided by the average of the IELT at the beginning of the treatment that served as a baseline (period A).

The Mahalanobis distance test will be used to check the existence of outliers (with a Z score of > 3) and the Kolmogorov-Smirnov test to check the goodness of fit of the data and the Square Root Transformation in those cases where the assumption of normality is not met.

The Greenhouse-Geisser method will be used to correct for degrees of freedom when the sphericity assumption is not met.

The MANOVA contrast will be performed for the demographic variables, and, presumably, we will find significant differences in variables such as age.

For the contrasts, ANCOVAs of independent measurements will be used, with the variables that have come out as significant in the MANOVA contrast as covariates, to check the differences between the two experimental groups and the equality between baselines in each of the study variables. And, similarly, ANCOVAs of repeated measurements to check the existence of the benefits of each therapy on the baseline.

All p values should be bilateral and the significance level used < 0.05. The IBM SPSS Statistics version 22 statistical package should be used.

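### ANCOVA covariates are chosen by significance tests between randomised groups, and baseline IELT enters the group comparison only as the fold-change denominator, never as a covariate

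*Protocol*

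**What the plan says.** Section 9 says of allocation: "The participants who meet the selection criteria will be randomly assigned to an experimental group, along with its corresponding conditions". Section 5.8 says the same.

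Section 14 then sets out the analysis in this order:

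- The main parameter is a fold change in IELT: the geometric average after treatment "divided by the average of the IELT at the beginning of the treatment that served as a baseline (period A").
- "The MANOVA contrast will be performed for the demographic variables, and, presumably, we will find significant differences in variables such as age". The variables are not listed and the grouping factor is not named. A comparison between the two randomised groups is the natural reading.
- ANCOVAs for independent measurements follow, "with the variables that have come out as significant in the MANOVA contrast as covariates". Their purpose is "to check the differences between the two experimental groups and the equality between baselines in each of the study variables".
- Within each therapy the plan uses "ANCOVAs of repeated measurements to check the existence of the benefits of each therapy on the baseline".
- On the error rate: "All p values should be bilateral and the significance level used < 0.05".

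No baseline value of IELT, PEP or GRISS is named as a covariate anywhere.

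**The concern.** A demographic difference between randomised groups arises by chance, so the statement that "presumably, we will find significant differences in variables such as age" has no basis in the design. A test of that difference does not show whether the variable predicts IELT, and only prediction makes a covariate useful. Under this rule a strongly prognostic variable that happens to be balanced is left out, and an irrelevant one that happens to be imbalanced is put in. The adjusted model is unknown until the data are seen.

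The screen covers demographics only, so no baseline outcome value can ever pass it. Baselines are instead tested for equality between groups, which answers no question when allocation is random. At stake is the precision of the comparison between SCT alone and SCT with the device, in a small trial that expects heavy losses.

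**Working it through.** **Inputs.** From the protocol: 24 per group, power 0.80 and alpha 0.05 (Section 12); 50 men and 30% dropout or non-compliance (Section 5.11); two-sided tests (Section 14). Assumed because the protocol does not give them: 1:1 allocation, the number of demographic variables, analysis of the fold change on the log scale, and the correlation ρ between log baseline and log post-treatment IELT.

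**The plan's own figure.** No effect size or SD is stated, so 24 per group cannot be reproduced, only inverted. The normal approximation gives d = (1.960 + 0.842) × √(2/24) = 0.81; the t-based value is 0.83. This is the standardised difference that 24 per group can detect.

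**How often chance supplies a covariate.** For k independent univariate tests, P(at least one significant) = 1 − 0.95^k:

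| k | 1 | 3 | 5 | 8 |
|---|---|---|---|---|
| P | 5% | 14% | 23% | 34% |

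If univariate results count only after a significant overall MANOVA, these figures are lower. Section 14 does not say which applies.

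**What the fold change costs.** Take the log-scale variance as 1 at both times. The log fold change then has variance 2(1 − ρ), and ANCOVA with log baseline has residual variance 1 − ρ². The ratio is (1 − ρ²)/[2(1 − ρ)] = (1 + ρ)/2.

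| ρ (assumed) | Log fold change | ANCOVA | Ratio | Cut |
|---|---|---|---|---|
| 0.3 | 1.40 | 0.91 | 0.65 | 35% |
| 0.5 | 1.00 | 0.75 | 0.75 | 25% |
| 0.7 | 0.60 | 0.51 | 0.85 | 15% |

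The gain shrinks as ρ approaches 1, because a slope fixed at 1 is then nearly right. With unequal SDs (s1 at baseline, s2 after), the excess variance of the fold change is (s1 − ρ·s2)². It is never negative, but it vanishes when s1 = ρ·s2.

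**Power.** Suppose 24 per group gives exactly 80% for the unadjusted log fold change (t-based d = 0.826). Losing 30% of 50 leaves 35 men; take 17 per group. The noncentrality is 0.826 × √(17/2) = 2.41 unadjusted, divided by √((1 + ρ)/2) when adjusted, with one further degree of freedom spent.

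| | Unadjusted | ρ = 0.3 | ρ = 0.5 | ρ = 0.7 |
|---|---|---|---|---|
| 17 per group | 0.65 | 0.82 | 0.77 | 0.72 |
| 24 per group | 0.80 | 0.93 | 0.90 | 0.86 |

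The normal approximation agrees to within about 0.01. Equivalently, 80% power would need 24 × (1 + ρ)/2 = 15.6, 18 or 20.4, that is 16, 18 or 21 per group.

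**Does the screen help or harm?** This was simulated with 24 per group, five independent demographics screened at 0.05, one of them prognostic (coefficient 0.3 SD), and 4,000 runs per setting:

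| Power at ρ = | 0.3 | 0.5 | 0.7 |
|---|---|---|---|
| Fold change, no covariates | 0.74 | 0.75 | 0.72 |
| Fold change, screened covariates | 0.73 | 0.74 | 0.72 |
| Baseline as covariate | 0.89 | 0.84 | 0.78 |
| Baseline plus the prognostic demographic, prespecified | 0.91 | 0.87 | 0.83 |

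Power without covariates is below 0.80 here because the prognostic demographic adds variance. With no true effect, the screened analysis rejected in 0.044 to 0.053 of runs across 24 and 17 per group. The screen therefore buys nothing and does not disturb the error rate.

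**The case against.** The best defence is that the plan does use baseline IELT. It is the denominator of the main parameter and the reference level in the repeated-measures analyses, and Section 10 defines added efficacy as a greater increase. This stands. A reader might infer that baseline information is discarded, and Section 14 contradicts that. Nor does the protocol support calling baseline IELT the strongest predictor, since it gives no correlation. For the same reason, the gain should be measured against the log fold change. A comparison of post-treatment values alone is not the planned main parameter, and gains against it rise with ρ when the true gain falls.

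It can also be said that the selection rule is written down beforehand, so nobody picks covariates freely afterwards. This stands in part: the rule is fixed, but the model it produces is not. A reader might infer an inflated type I error, and the simulation shows none.

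Finally, Section 13 limits entry to a mean IELT below 120 seconds. That may narrow the baseline spread relative to the post-treatment spread and make the gain smaller than the equal-variance table shows. This stands as a limit on the size, not on the direction.

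None of this rescues the screen itself. A separate SAP would not excuse it either, because the protocol states the rule outright.

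**Conclusion.** The point holds in two parts. First, the ANCOVA covariates are decided by chance imbalance in unlisted demographics, so the adjusted model is not fixed in advance and is not chosen for prognostic value. Second, baseline IELT has its log-scale slope fixed at 1 in the group comparison and is never a covariate. For PEP and GRISS no fold change is defined, and the group contrasts name no baseline covariate.

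The cost is precision: 15% to 35% of the residual variance for ρ between 0.7 and 0.3, or about 7 to 17 percentage points of power at 17 per group. These sizes rest on an assumed ρ, equal log-scale variances, log-scale analysis of the fold change, and 24 per group being an 80% design for that endpoint. The documents do not support a claim of bias or of excess false positives. The change is worth making because it is free, but the defect does not invalidate the trial.

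**What to change.** In Section 14, delete the MANOVA screen, the expectation of an age difference and the tests of baseline equality. In their place:

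- **IELT:** prespecify an ANCOVA of log fold change on treatment group, with log baseline IELT (the same average that forms the denominator) as covariate. Since log post = log fold change + log baseline, this gives the same treatment estimate as an ANCOVA of log post-treatment IELT; only the baseline coefficient shifts by 1. The declared main parameter is kept.
- **PEP and GRISS:** use each scale's own baseline value as covariate.
- **Demographics:** if age or another variable is thought prognostic, name it now and keep it whatever the observed balance. Show demographics by group without p-values.

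The cost is a rewording of Section 14 and one degree of freedom per covariate. The baseline values are already to be collected.

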Ingredients: Water, Propylene Glycol Hydroxycyclulose, Sodium Benzoate, Polysorbate 20, Potassium Sorbate, D-limonene, Sodium Hydroxide, Carica Papaya

Fruit Extract, Chamomilla Recutita, Flower Extract, Citric Acid, Plankton Extract, Perfume, Sodium Citrate, Citral, Soluble Collagen.

5.11. **Sample group and number of participants.**

The sample group will be heterosexual men, aged 18 or older, taken from all over the country. They all suffer from primary premature ejaculation, haven't received any treatment for the condition in the past, and have had a stable partner for at least 3 months before the start of the trial.

A sample size of 50 patients is expected. We estimate a 30% dropout or non-compliance during the study.

5.12 **Schedule and proposed end date**

Duration of the inclusion period: June 2019 - August 2019

Planned trial start date: July 2017

Planned trial end date: September 2017

5.13. **Financing**

Funding will be provided by the research area of the Sexological Institute, Murcia, Spain, and the NEW WELLNESS CONCEPT SL.

6. **RELEVANT FINANCIAL ASPECTS OF THE TRIAL**

50% of the project's funding will be provided by the research area of the Sexological Institute, Murcia, Spain, while the other 50% will be funded by the NEW WELLNESS CONCEPT SL.

This 50 % includes the provision of 30 Myhixel I devices and 30 bottle of lubricant Myhixel lube.

FINANCIAL REPORT ON THE PROJECTED EXPENDITURE OF THE RESEARCH PROJECT:

Title: **PROTOCOL INVESTIGATION: MYHIXEL**

Research code: **ISM-SCT-2019-01**

Lead Researcher: **[name]**

Promoter: **Sexological Institute, Murcia, Spain**

DETAILED DESCRIPTION OF PROJECTED FUNDED COSTS

COSTS PERSONNEL:	
1 Part-time Research Intern	400,00 €/month *
SUBTOTAL PERSONNEL:	1.200 ,00 €
FACILITIES, MATERIALS, SOFTWARE LICENSES AND TESTS:	
Licenses and correction kit MCMI-III, PEP, PEDT y GRISS male.	66,49 €
1 monthly license IBM SPSS statistics software.	88,50 €
MRW Courier Service ecommerce National Transport 30 kits	275,10 €
SUBTOTAL FACILITIES AND EQUIPMENT:	430,09 €
CONSUMIBLES:	
50 Myhixel lubricant (HOLE LOTION)	480,00 €
30 Myhixel Device	990,00€
SUBTOTAL CONSUMIBLES:	1470,00€

OTHER COSTS: (specify details of costs and amounts paid)	
Domain and hosting, web landing page for trial, yocontrolo.org, Arsys S.L.U.	101,41€
Online templates Web Templates Ltd	67,00 €
SUBTOTAL OTHER COSTS:	2043,91 €
TOTAL PROJECT BUDGET:	5.419,10 €

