12. SAMPLE GROUP AND TOTAL NUMBER OF PARTICIPANTS

The subjects to be considered will be all those interested in participating who respond to the national advertising campaign that will be launched. They will be contacted by e-mail or telephone, and the questionnaires and selection records will be sent by e-mail (the criteria for inclusion in the study are defined in the following section).

All patients who come to the MSI requesting evaluation and treatment for PE and who meet the inclusion criteria will also be able to participate in the study. Subjects will be free to leave the study at any time and will not receive financial compensation for participating, although they will receive a gift at the end of the study, and a high drop-out rate is expected.

Based on randomized studies to assess the efficacy of treatments for premature ejaculation in which there was a control group, we estimate that 24 subjects per group will be needed to establish the differences between the two groups, considering a statistical power of 0.80 and alpha of $p=0.05$.

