19. INTERVIEWS, QUESTIONNAIRES OR INSTRUMENTS TO BE USED IN THE TRIAL

The IELT measurements will be collected by self-registration after each week of treatment (APPENDIX I).

In order to collect the information regarding the perception of ejaculation, the Premature Ejaculation Profile (PEP) will be used (Patrick et al., 2009), a self-reported instrument consisting of four measurements (perceived control over ejaculation, personal stress related to ejaculation, satisfaction with sexual relationships, and interpersonal difficulty related to ejaculation). These will give an overall profile and score (Patrick et al., 2009), where the lowest scores express the lowest performance. The reliability coefficient between ranges from 0.66 to 0.83 and its validity was contrasted with dapoxetine and Intravaginal Ejaculation Latency Times (IELT). This instrument was validated in American and European trials, with people from Germany, France, England, Italy and Poland involved (Giuliano et al., 2008) although it has been used also in the Spanish community (Bar-Or, Salottolo, Orlando, Winkler, & Group, 2012; Buvat, Tesfaye, Rothman, Rivas, & Giuliano, 2009).

The Premature Ejaculation Diagnostic Tool (PEDT) will be used for the diagnosis. It takes five measurements in order to evaluate difficulty in delaying the ejaculation, ejaculation occurring before the patient wanted it, ejaculation with little stimulation, frustration related to premature ejaculation, and the couple's opinion about ejaculation. The test-retest reliability is 0.82 and all values statistically distinguish and differentiate statistically between PE and non-PE patients.

The Golombok-Rust Inventory of Sexual Satisfaction (GRISS) will also be applied. This is a brief 28-question questionnaire to assess the existence and severity of sexual problems in both members of a heterosexual relationship (Rust & Golombok, 1985, 1986). This questionnaire provides separate scores for men and women on 3 shared scales (avoidance, non-sensitivity, and dissatisfaction) and 6 gender-specific scales (impotence, premature ejaculation, anorgasmia, vaginismus, infrequency, and lack of communication) with acceptable values of reliability and validity (Rust & Golombok, 1985, 1986). The instrument was validated in the English community and is already being used in Spain in the official Master's degree in Sexology at the University of Almeria (García González, 2013; López Lorente, 2013).

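### The ANCOVAs fixed in section 14, as commonly run, omit men without period B data; with 30% dropout or non-compliance expected, the device comparison can be biased if leaving depends on response differently in the two arms

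*Protocol*

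**What the plan says.** Section 14 makes the IELT fold change the main parameter: a geometric average for period B, after treatment, divided by the baseline average for period A. The device effect is tested by an independent-measures ANCOVA between the two groups. The within-arm benefit is tested by "ANCOVAs of repeated measurements to check the existence of the benefits of each therapy on the baseline". A Greenhouse-Geisser correction is foreseen. On error rates the section says "All p values should be bilateral and the significance level used < 0.05".

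On numbers, section 5.11 says "A sample size of 50 patients is expected" and "We estimate a 30% dropout or non-compliance during the study". Section 12 adds that "a high drop-out rate is expected" and states: "we estimate that 24 subjects per group will be needed to establish the differences between the two groups", "considering a statistical power of 0.80".

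On data, section 19 says "The IELT measurements will be collected by self-registration after each week of treatment (APPENDIX I"). Section 16 sets treatment at 7 weeks, and section 9 collects baseline data over a period of similar length.

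The protocol does not say which weeks make up period B.

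**The concern.** A fold change needs both periods. A man with no period B record has no value for the main parameter and does not enter the between-arm ANCOVA unless something is imputed. The classical repeated-measures ANCOVA has the same limit, and it is stricter if weeks are its levels, because one missing week removes the man. The protocol thus predicts heavy loss and names methods that by default analyse only those who remain.

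Randomisation protects the comparison of all men assigned, not of those who stay. Loss linked to response is plausible here. Appendix 3 lets a man start the later exercises only once he has reached the earlier objectives, so a man who responds poorly may stall or leave. Section 17 removes men with lubricant irritation from the study. The arms differ in whether a device is used, so reasons for leaving may differ too. If they do, a device effect can appear, or be hidden, through selection alone. Meanwhile the weekly register may already hold several records from each man who leaves.

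**Working it through.** **1. The plan's own figure.** Section 12 gives 24 per group at power 0.80 and alpha 0.05 (two-sided, section 14), but no effect size or SD, so the figure can only be back-solved. The implied standardised difference is d = (1.960 + 0.842) × √(2/24) = 0.81 by the normal approximation, or 0.83 by the t distribution.

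**2. What a 30% loss would leave.** 50 × 0.70 = 35 men, or 17.5 per arm against the 24 required. If the whole 30% were lost to analysis, power at the implied d would fall from 0.80 to about 0.66–0.67. This is an upper bound on the damage, because the 30% includes non-compliance.

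**3. If weeks are the repeated levels.** IELT needs intercourse, so gaps are likely. If each week had a 5% or 10% chance of no record (assumed), the share of men with all seven weeks would be 0.95⁷ = 0.70 or 0.90⁷ = 0.48, before any dropout.

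**4. When omission biases the device contrast.** All inputs here are assumptions, not document figures:

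- log IELT with between-man SD 0.5 at baseline, 0.5 for response and 0.3 for the weekly residual
- an average threefold gain reached linearly over 7 weeks
- no true device effect
- loss after week 3, depending (where stated) on the change recorded in weeks 1–3
- period B taken as week 7
- 200,000 men per arm, so that only bias is seen

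| Loss SCT / device | Link of leaving to poor early response | Completer ratio, device/SCT | Ratio using leavers' weeks 1–3 |
|---|---|---|---|
| 30% / 30% | none | 1.00 | 1.00 |
| 20% / 40% | none | 1.00 | 1.00 |
| 30% / 30% | same in both arms | 1.00 | 1.00 |
| 20% / 40% | same in both arms | 1.05 | 1.00 |
| 20% / 40% | same, stronger | 1.08 | 1.00 |
| 40% / 20% | same in both arms | 0.95 | 1.00 |
| 10% / 50% | same in both arms | 1.12 | 1.00 |
| 30% / 30% | device arm only | 1.11 | 0.99 |

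A difference in dropout rate is neither sufficient for bias (row 2) nor necessary (last row). Bias needs leaving to be related to response, with either the rate or that relation differing by arm.

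**5. At trial size.** 25 per arm, the same SDs, no true effect, completer ANCOVA:

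| Loss pattern | Ratio | Type I error |
|---|---|---|
| 30% each arm, random | 0.99 | 5% |
| 30% each, device-arm selection weak / moderate / strong | 1.06 / 1.10 / 1.14 | 5.5% / 7% / 9% |
| Losses of 30% and 34%, response-related in device arm | 1.16 | 11% |
| About 30% each, weekly device-arm dropout following the previous week's change, milder / stronger | 1.13 / 1.21 | 8% / 11% |
| As above, 38% loss in the device arm | 1.23–1.26 | 14% |

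**6. Does a mixed model on the weekly values help?** It depends on the covariance.

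- **Random intercept only.** Type I error for the week-7 contrast was about 13% with no dropout and 15% with random 30% loss, where the completer ANCOVA held about 5%. Under response-related loss it still showed a ratio of 1.08.
- **Random intercept and slope.** The ratio was about 1.01 and type I error 3–8% under response-related loss. Under random loss the SD of the log ratio was 0.198 against 0.242 for completers: (0.198/0.242)² = 0.67, about one third less variance. Some fits gave convergence warnings.

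**The case against.** The strongest reply is that section 14 names tests, not an analysis set. ANCOVA can be run after imputation, and analysis sets and missing-data rules are usually left to the SAP, which is not shown. This stands as far as silence goes: the missing rule is not the point. The point is that the named outcome and the named classical tests need a period B value, and a method that does not need one is available from data already collected.

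Four stronger readings that a reader might infer are not supported:

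- **That the weekly records are thrown away.** No section says so. Period B is an average not tied to weeks, and the Greenhouse-Geisser rule has a role only with three or more repeated levels. If weeks are those levels the records are used, but a man missing any week is still deleted.
- **That only compliant men are analysed.** Section 5.11 counts dropout and non-compliance together but does not remove non-compliers from the analysis. Pure loss may be well below 30%.
- **That unequal dropout by itself biases the device effect.** The second row of the first table shows it does not. The protocol gives no split of dropout by arm and no evidence that leaving will be related to response differently by arm.
- **That the sentence on repeated-measures ANCOVAs is the device test.** It is the within-arm test. The device effect is tested by the independent-measures ANCOVA named just before it, which has the same limit.

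It is also fair to say that the simulations favour the mixed model. Dropout was made to depend on recorded values, response was linear, and the completer analysis used week 7 alone, so part of the gain in precision may come from comparing one week with seven.

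**Conclusion.** The concern holds as a risk, not a demonstrated bias. Section 14 fixes methods that, as commonly run, leave out men without period B data, in a trial that expects 30% dropout or non-compliance. The device comparison can be biased if leaving depends on response differently in the two arms.

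With assumed log SDs of 0.5, 0.5 and 0.3, no true effect, about 30% loss and response-related loss in the device arm, the completer ratio is about 1.05–1.15, with type I error of about 5–11%. Stronger selection or heavier device-arm loss takes these to about 1.25 and 14%. If more SCT men leave for poor response, the bias runs the other way (0.95 in the case computed). A different definition of period B would change these sizes.

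The section should be changed. The defect does not make the trial uninterpretable.

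**What to change.** In section 14, for IELT:

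- Replace the two-period ANCOVA with a mixed model for repeated measures on each man's weekly log(IELT), with arm, week, arm-by-week and baseline log(IELT) as fixed effects.
- Use an unstructured within-man covariance. Seven weeks need 7 × 8 / 2 = 28 covariance parameters from about 50 men, so name a random intercept and slope as the fallback if it does not converge. Do not use a random intercept alone. Use Satterthwaite or similar small-sample degrees of freedom.
- Include every randomised man in his assigned arm, whatever his compliance, with all the weeks he recorded. State that men who stop early are asked to keep returning the register.
- State which weeks form period B and make the model's between-arm contrast target that period. If period B lies after week 7, its records must be added to the model as later time points.
- Keep the completer ANCOVA as a sensitivity analysis.

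The cost is a change of wording; the data are already planned. Two limits remain. The result rests on a missing-at-random assumption, and the sponsor must confirm that the SPSS licence in the section 6 budget includes mixed models. The unstructured version was not simulated here, so its convergence and type I error at this sample size should be checked before it is fixed.
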